2. STUDY OBJECTIVES

2.1. Primary Objective

The primary objective is to evaluate the safety and efficacy of 2 different concentrations of AZR-MD-001 ointment/semi-solid drug applied to the lower lid twice-weekly for up to 6 months, as compared to placebo, in patients with MGD.

2.2. Brief Description

The study is a multi-center, double-masked, placebo-controlled, randomized, parallel group study carried out in 2 sequential cohorts. The Expansion Cohort includes parallel doses of 2 concentrations of AZR-MD-001 ointment/semi-solid drug (0.5% and 1.0%) and placebo, dosed twice-weekly in the evening. Patients are to be followed for 6 months. Primary efficacy analyses will be performed based on the 3-month data, and exploratory efficacy analyses will be performed on data collected during the subsequent 3-month safety follow-up.

Inclusion and exclusion criteria are provided in [AZ201801 Protocol Sections 5.1](#) and [Section 5.2](#).

Key inclusion criteria require patients have meibomian gland secretion (MGS) scores of ≤ 12 in both eyes at the Screening and Baseline visits; reported dry eye signs and symptoms within the past 3 months; Standard Patient Evaluation of Eye Dryness questionnaire (SPEED) score ≥ 6 ; OSDI questionnaire total score ≥ 13 and < 34 ; and tear break-up time (TBUT) < 10 seconds in both eyes.

Exclusion criteria include best corrected visual acuity (BCVA) worse than 20/40 in either eye; anticipated contact lens use; Schirmer's tear test without anesthesia ≤ 5 mm in either eye at the baseline visit; or corneal staining ≥ 3 (between 33 and 100 dots) using the Oxford Scheme.

2.3. Determination of Sample Size

2.3.1. Initial Determination of Sample Size

Estimates for Expansion Cohort sample size calculations are from the integrated analysis of AZ201801 Cohort 1, AZ202001, SOVS2019-070, and SOVS2020-080, limited to the mITT Analyzable population (refer to the [integrated Clinical Study Report](#)). The means and standard deviations of the changes from baseline at Month 3, after applying last observation carried forward (LOCF) imputation, are utilized ([Table 1](#)).

Table 1 Integrated Analyses Change from Baseline to Month 3

	AZR-MD-001 0.5% Mean (SD)	AZR-MD-001 1.0% Mean (SD)	Placebo Mean (SD)
MGYLS	2.77 (3.35)	3.79 (4.11)	0.77 (2.28)
OSDI	-8.36 (9.06)	-5.33 (8.39)	-0.81 (6.31)

Abbreviations: MGYLS = meibomian glands yielding liquid secretion; OSDI = Ocular Surface Disease Index; SD = standard deviation.

The study was designed to have 95% power to detect treatment differences between AZR-MD-001 0.5% and placebo, and between AZR-MD-001 1.0% and placebo, which requires 72 patients per treatment arm. To allow for additional site-to-site variability, the sample size per group was increased to 75 randomized patients per arm.

The total number of randomized patients for the Expansion Cohort will be approximately 225 (75× 3). Approximately 112 patients should have a baseline MGS score of <6 and approximately 112 patients should have a baseline MGS score ≥6 and ≤12. Based upon data from the LipiFlow® development program, a screen failure rate of ~ 40% is expected. Thus, ~315 patients will need to be screened to achieve ~225 patients randomized to treatment.

2.3.2. Sample Size Re-Estimation

As described in [Section 1.2](#), additional patients may be enrolled if the observed variability within the Expansion Cohort is higher than anticipated, after the evaluation of the MGYLS and OSDI total score changes from baseline to Month 3 using LOCF imputation. The standard deviation of the pooled treatment groups will be calculated in a masked fashion for both MGYLS and OSDI total score and compared to the pooled standard deviations of 3.63 (MGYLS) and 8.71 (OSDI) from the integrated study. No unmasking will be performed as part of this re-estimation.

The power calculations from the integrated studies will be re-derived based on pooled standard deviations (resulting in 0.918 for the MGYLS comparison of AZR-MD-001 0.5% to placebo, and >0.999 for the other comparisons), for the sole purpose of providing a basis for comparison to the power re-calculations based on the pooled standard deviations from the Expansion Cohort.

Patients may be added up to the specified numbers, to maintain the current power of the study, if possible. For example:

- If the pooled standard deviation is 3.64-3.85 for MGYLS or 8.72-9.64 for OSDI total score, up to 30 additional patients may be randomized (10 per treatment arm).
- If the pooled standard deviation is 3.86-4.07 for MGYLS or 9.65-10.20 for OSDI total score, up to 60 additional patients may be randomized (20 per treatment arm).
- If the pooled standard deviation is 4.08-4.29 for MGYLS or 10.21-10.74 for OSDI total score, up to 90 additional patients may be randomized (30 per treatment arm).

The specific sample sizes needed will be recalculated using the initial mean changes from baseline from the integrated studies, in conjunction with the pooled standard deviations from the Expansion Cohort, using the following pseudocode:

```
proc power;
  twosamplemeans test=diff dist=normal groupmeans=(2.77 0.77)
  stddev=xxx sides=2 power=.918 npergroup=.;
run;
proc power;
  twosamplemeans test=diff dist=normal groupmeans=(3.79 0.77)
  stddev=xxx sides=2 power=.999 npergroup=.;
run;
proc power;
  twosamplemeans test=diff dist=normal groupmeans=(-8.36 -0.81)
  stddev=xxx sides=2 power=.999 npergroup=.;
run;
proc power;
  twosamplemeans test=diff dist=normal groupmeans=(-5.33 -0.81)
  stddev=xxx sides=2 power=.999 npergroup=.;
run;
```

If additional patients are added, the database freeze and unmasking of specific team members will be postponed until after those patients complete their Month 3 visit.

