8.1.1. Primary Efficacy Endpoints

The primary efficacy variables are:

- change from baseline to Month 3 in MGYLS
- change from baseline to Month 3 in OSDI total score

The primary efficacy endpoints will be evaluated using the following hierarchical approach. For each endpoint, the subsequent endpoint will not be evaluated unless the prior endpoint is significant at $\alpha=0.05$. Therefore, this hierarchical approach controls for the family-wise Type I error and does not require adjustment for multiplicity, as per [Dmitrienko and D'Agostino, 2013](#).

- a) Change from baseline to Month 3 in MGYLS, comparing AZR-MD-001 0.5% to placebo.
- b) Change from baseline to Month 3 in OSDI total score, comparing AZR-MD-001 0.5% to placebo.
- c) Change from baseline to Month 3 in MGYLS, comparing AZR-MD-001 1.0% to placebo.
- d) Change from baseline to Month 3 in OSDI total score, comparing AZR-MD-001 1.0% to placebo.

Multiple imputation will be applied, as described in [Section 5.3](#). Analyses will be performed as follows.

Change from baseline in MGYLS will be analyzed at Month 3 using an ANCOVA model with (continuous) baseline MGYLS score as a covariate and treatment (AZR-MD-001 ointment/semi-

solid drug or placebo), duration of disease category (i.e., <5 or ≥ 5 years), and baseline MGS score category (< 6 or ≥ 6 and ≤ 12) as factors in the model. This ANCOVA model will also be performed for each AZR-MD-001 ointment/semi-solid drug dosing level versus placebo. The least square means for the differences between treatments will be presented along with two-sided (95%) confidence intervals.

The following pseudocode will be used:

```
PROC GENMOD data=xxx;  
  BY visit;  
  CLASS treatment (ref = 'AZR-MD-001 PLACEBO') duration baseMGS;  
  MODEL chg =treatment base duration baseMGS;  
  LSMEANS treatment;  
run;
```

Change from baseline in OSDI total score will be analyzed at Month 3 using the same methodology as the change from baseline in MGYLS, using an ANCOVA model with (continuous) baseline OSDI total score as a covariate and treatment, duration of disease category, and baseline MGS score category as factors in the model.

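### SAP 2.3.2 gives power above 0.999 for OSDI 1.0% versus placebo; its own inputs give 0.884, and the wrong value is coded as a re-estimation target

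*SAP*

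**What the plan says.** Section 2.3.1 of the SAP plans for 95% power on both active-versus-placebo comparisons, "which requires 72 patients per treatment arm", raised to 75 for site-to-site variability. Its Table 1 gives the means and SDs by arm.

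Section 2.3.2 provides for a masked re-estimation. Pooled SDs of 3.63 (MGYLS) and 8.71 (OSDI) are the reference, and power is re-derived from them, "resulting in 0.918 for the MGYLS comparison of AZR-MD-001 0.5% to placebo, and >0.999 for the other comparisons". The pseudocode has four calls, so the other comparisons are MGYLS 1.0%, OSDI 0.5% and OSDI 1.0%. The last is coded as "twosamplemeans test=diff dist=normal groupmeans=(-5.33 -0.81") with power=.999.

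Additions are capped: "Patients may be added up to the specified numbers, to maintain the current power of the study, if possible". The first band reads "If the pooled standard deviation is 3.64-3.85 for MGYLS or 8.72-9.64 for OSDI total score, up to 30 additional patients may be randomized", which is 10 per arm. The third ends with "10.21-10.74 for OSDI total score, up to 90 additional patients may be randomized (30 per treatment arm"). The limits are therefore 85, 95 and 105 per arm.

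Section 8.1.1 places this comparison last in the fixed sequence, as step (d): "Change from baseline to Month 3 in OSDI total score, comparing AZR-MD-001 1.0% to placebo".

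**The concern.** OSDI 1.0% has a planned difference of 4.52 and OSDI 0.5% one of 7.55. Both are set against the same SD of 8.71, so they cannot be expected to have nearly the same power. Section 2.3.1 points the same way. Its 72 per arm for 95% power can be recovered only from OSDI 1.0%, using a smaller SD. Power cannot then rise above 0.999 when the SD increases.

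The re-derived powers are the yardstick for judging whether patients should be added, and the fourth one is also a number in the code. If it is wrong, a reader will believe that step (d) starts from, and is being held at, a power it never had. The fourth call will also ask for a sample size unrelated to the reference design of 75 per arm.

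**Working it through.** **Inputs.** Means and pooled SDs are from SAP 2.3.2, and 75 per arm is from 2.3.1. The pseudocode states no alpha. I take two-sided 0.05, the level in 8.1.1.

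**Formula.** Two-sample t-test with n per arm: noncentrality λ = δ / (SD × √(2/n)), df = 2n − 2. Power is the probability that a noncentral t variable with parameter λ falls outside ± the critical value. For n = 75, √(2/75) = 0.1633, df = 148 and the critical value is 1.976.

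**The four re-derived powers**

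| Comparison | δ | SD | λ | Power | SAP |
|---|---|---|---|---|---|
| MGYLS 0.5% | 2.77 − 0.77 = 2.00 | 3.63 | 3.374 | 0.9180 | 0.918 |
| MGYLS 1.0% | 3.79 − 0.77 = 3.02 | 3.63 | 5.095 | 0.9990 | >0.999 |
| OSDI 0.5% | 8.36 − 0.81 = 7.55 | 8.71 | 5.308 | 0.9995 | >0.999 |
| OSDI 1.0% | 5.33 − 0.81 = 4.52 | 8.71 | 3.178 | **0.8844** | >0.999 |

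The exact match at 0.918 confirms the method, the alpha and n = 75. MGYLS 1.0% is 0.99904 before rounding, so it also agrees.

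**Could another basis give >0.999 for OSDI 1.0%?** No basis tried does: 72 per arm gives 0.871, a one-sided test 0.936, the Table 1 pairwise SD 0.959, the root-mean-square SD of the three arms (8.01) 0.930, and 150 active versus 75 placebo 0.955. Reaching 0.999 at 75 per arm needs an SD of about 5.44 or a difference of about 7.24.

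**Cross-check against 2.3.1.** Pairwise SD for OSDI 1.0% = √((8.39² + 6.31²)/2) = 7.42. Power is 0.9498 at 71 per arm, 0.9524 at 72 and 0.959 at 75. The other three comparisons need 55 (MGYLS 0.5%), 33 (MGYLS 1.0%) and 29 (OSDI 0.5%) per arm for 95%. OSDI 1.0% is therefore the only comparison that yields 72.

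**What the calls return (n per arm)**

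| OSDI SD | Limit | OSDI 1.0% at .999 | OSDI 1.0% at .884 | OSDI 0.5% at .999 |
|---|---|---|---|---|
| 8.71 (reference) | 75 | 191 | 75 | 69 |
| 9.64 (band 1 top) | 85 | 233 | 92 | 85 |
| 10.20 (band 2 top) | 95 | 261 | 103 | 95 |
| 10.74 (band 3 top) | 105 | 289 | 114 | 105 |

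As coded, the fourth call exceeds 105 at every OSDI SD that triggers a band. If only MGYLS triggers, it still exceeds 105 unless the OSDI SD is about 6.45 or less. With the target at .884, it stays within the limits up to SDs of 9.28, 9.82 and 10.33. The band tops agree with the OSDI 0.5% column.

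**OSDI 1.0% power with full additions.** On the pooled-SD basis: 0.860 (SD 9.64, 85 per arm), 0.860 (10.20, 95) and 0.859 (10.74, 105). A masked SD also contains the spread between arm means. With equal arms and the Table 1 means, that variance is 9.62. Removing it gives within-arm SDs of √(9.64² − 9.62) = 9.13, then 9.72 and 10.28, and powers of 0.894, 0.891 and 0.887.

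**The case against.** The SAP says the re-derived powers serve only as a basis for comparison. The design power is the 95% of 2.3.1, and that figure is sound for OSDI 1.0%. Additions are optional and capped, so 191 to 289 per arm would not be enrolled under the bands. If the largest call governs, the inflated target pushes enrolment to the band limit, which helps this comparison. At an OSDI SD of 8.72, 85 per arm gives power 0.919, whereas the corrected call asks for 76 and gives 0.888. The comparison is also last in the hierarchy.

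These points stand, and they limit the consequence. They do not defend the figure: the comparison basis is what is wrong, and the same value is coded as a target. Because the limits are maxima, the calls are meant to choose a number within them, and the fourth cannot.

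Three narrower points are also fair. The entry for MGYLS 1.0% is true as written, so restating it as 0.999 is optional. The 0.89 figure depends on the Table 1 means recurring in equal arms; that calculation gives a combined reference SD of 8.59 where the SAP has 8.71, and the integrated arm sizes are not in the documents. Finally, the SAP does not say which of the four calls governs. That gap is separate, and the corrected target does not depend on it.

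**Conclusion.** The concern holds. For OSDI 1.0% versus placebo the stated power is above 0.999. On the SAP's own basis it is 0.884, at least 11.5 percentage points lower. The assumptions are those of 2.3.2: a two-sample t-test, 75 per arm, SD 8.71, planned difference 4.52, and the two-sided 0.05 level of 8.1.1.

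The fourth call's result carries no information on the number of patients needed whenever OSDI triggers re-estimation. Type I error, masking, the final tests and hierarchy steps (a) to (c) are unaffected. The harm is a wrong benchmark for step (d) and an uninformative target. This should be fixed, but it does not threaten the trial's validity.

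**What to change.** In SAP 2.3.2:

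- Give the re-derived powers separately, all on the pooled-SD basis: 0.918 (MGYLS 0.5%), 0.999 (MGYLS 1.0%), >0.999 (OSDI 0.5%) and 0.884 (OSDI 1.0%).
- Set power=.884 in the fourth PROC POWER call. It then returns 75 per arm at SD 8.71.
- Keep the bands, and add one sentence: the OSDI bands match the 0.5% comparison; the band maximum applies where a call exceeds it; and with full additions OSDI 1.0% power is about 0.86 at the band tops on the pooled-SD basis (about 0.89 if the planned between-arm variance is removed from the masked SD).

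Make the change before the masked re-estimation, so that the target is not altered once the observed SDs are known.

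The editing cost is small, with two downsides. The published OSDI 1.0% power becomes less favourable. Low in each band the corrected call may ask for fewer patients than the limit: 76 against 85 per arm at OSDI SD 8.72, 92 against 95 at 9.65, and 103 against 105 at 10.21. If only MGYLS triggers, the corrected call returns 75 or fewer and the MGYLS calls set the addition, for example 76 against 85 at an MGYLS SD of 3.64.

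### The benchmark powers in SAP 2.3.2 are unlabelled stand-alone figures: the one for OSDI 1.0% is wrong (0.884, not >0.999), and under the fixed sequence no later step can exceed 0.918

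*SAP*

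**What the plan says.** SAP 2.3.2 re-derives power from the integrated studies, "resulting in 0.918 for the MGYLS comparison of AZR-MD-001 0.5% to placebo, and >0.999 for the other comparisons". It states the role of these figures: they are given "for the sole purpose of providing a basis for comparison to the power re-calculations" based on the Expansion Cohort's own SDs. The reference SDs are 3.63 for MGYLS and 8.71 for OSDI. The next paragraph turns the figures into the target: "Patients may be added up to the specified numbers, to maintain the current power of the study, if possible". Three example brackets of observed SD then allow up to 10, 20 or 30 more patients per arm. Four separate PROC POWER calls follow, one with power=.918 (MGYLS 0.5%) and three with power=.999.

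SAP 8.1.1 sets the order of testing: (a) MGYLS 0.5%, (b) OSDI 0.5%, (c) MGYLS 1.0%, (d) OSDI 1.0%, each against placebo at 0.05. The rule is "For each endpoint, the subsequent endpoint will not be evaluated unless the prior endpoint is significant". SAP 2.3 does not mention this sequence and gives no joint power.

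**The concern.** Two things do not fit. First, one of the comparisons printed at >0.999 has a much smaller standardised difference than the other two, so the same figure for all three is doubtful. Second, a test that is carried out only after step a succeeds cannot be declared significant more often than step a. Printing >0.999 beside 0.918 without saying that these are stand-alone powers invites a reader to treat the later claims as near certain.

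The figures also drive a decision. The re-estimation is meant "to maintain the current power of the study, if possible". If the benchmark for one comparison is wrong, the code and the brackets disagree on how many patients are needed, and the team has no written rule to settle it.

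**Working it through.** **Inputs.** n = 75 per arm (SAP 2.3.1), two-sided 0.05, SDs 3.63 and 8.71, and the group means in the SAP 2.3.2 code. The differences are a: 2.77 − 0.77 = 2.00; b: −8.36 + 0.81 = −7.55; c: 3.79 − 0.77 = 3.02; d: −5.33 + 0.81 = −4.52.

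**Stand-alone power.** Two-sample t-test with 148 df and noncentrality |difference| / (SD × √(2/75)), where √(2/75) = 0.1633.

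| Step | Noncentrality | Power | SAP prints |
|---|---|---|---|
| a MGYLS 0.5% | 2.00 / 0.5928 = 3.37 | 0.918 | 0.918 |
| b OSDI 0.5% | 7.55 / 1.4223 = 5.31 | 0.9995 | >0.999 |
| c MGYLS 1.0% | 3.02 / 0.5928 = 5.09 | 0.9990 | >0.999 |
| d OSDI 1.0% | 4.52 / 1.4223 = 3.18 | 0.884 | >0.999 |

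The first three reproduce and d does not. For d, 72 per arm gives 0.871 and a one-sided 0.05 test gives 0.937. Reaching 0.999 at 75 per arm would need an SD of about 5.4. SAP 2.3.1 points the same way: its 72 per arm for 95% power is what d requires with the Table 1 SDs of 8.39 and 6.31 (root mean square 7.42; power 0.952 at 72 and 0.960 at 75). A larger SD of 8.71 cannot raise that to >0.999.

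**Sequence probability.** P(later step declared) ≤ P(a) = 0.918, and P(d declared) ≤ 0.884. Three arms sharing one placebo were simulated, with at least 200,000 runs per setting and the MGYLS–OSDI correlation assumed between 0 and 0.8:

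- through a: 0.918
- through b: about 0.918
- through c: about 0.917
- through d: 0.81 (correlation 0) to 0.83 (correlation 0.8)

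Whatever the correlation, d lies between 0.918 + 0.9995 + 0.9990 + 0.8844 − 3 = 0.80 and 0.884.

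**Do the brackets hold this?** At the upper limit of each bracket, with the maximum added patients:

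| n per arm | SDs (MGYLS / OSDI) | Stand-alone a, b, c, d | Through c | Through d, correlation 0 to 0.6 |
|---|---|---|---|---|
| 85 | 3.85 / 9.64 | 0.920, 0.999, 0.999, 0.860 | 0.92 | 0.79–0.80 |
| 95 | 4.07 / 10.20 | 0.921, 0.999, 0.999, 0.860 | 0.92 | 0.79–0.80 |
| 105 | 4.29 / 10.74 | 0.920, 0.999, 0.999, 0.859 | 0.92 | 0.79–0.80 |

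At correlation 0.8 the last column is about 0.81.

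**The power calls.** At OSDI SDs of 9.64, 10.20 and 10.74, the third call (difference 7.55, power .999) returns 85, 95 and 105 per arm, exactly the bracket steps. The fourth call (difference 4.52, power .999) returns 233, 261 and 289. At the reference SD of 8.71, where no bracket is triggered, it already returns 191. The OSDI brackets therefore fit only the 0.5% comparison.

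**The case against.** The strongest reply is that these are per-comparison powers, each from its own two-sample calculation and offered for a stated, narrow purpose. A stand-alone power is not made wrong by the test's place behind a gate. This stands for b and c: both figures reproduce, and nothing in the SAP promises joint power.

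A reader might also infer that holding four separate targets fails to hold the chance of success under the sequence. For a to c the documents do not support that. With a at 0.918 and b and c at 0.999, the chance of passing all three is at least 1 − 0.082 − 0.001 − 0.001 = 0.916 whatever the correlation, and at the bracket limits it is about 0.92. The .999 targets for b and c are what keep it there, so there is no case for dropping them.

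Nor does the point show an underpowered trial. The 0.918 belongs to the pooled SD of 3.63. With the Table 1 SDs at 75 per arm, step a has power 0.989 and all four steps succeed with probability of about 0.95, so the 95% in SAP 2.3.1 is roughly met on that basis.

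The reply does not reach step d, whose figure is wrong even as a stand-alone power, or the missing label on a benchmark that the next paragraph treats as the study's current power.

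**Conclusion.** The concern holds in a limited form, and it should be fixed before the masked re-estimation. One of the four benchmark figures is wrong: OSDI 1.0% is 0.884, about 11.5 points below the printed value. The other three are correct but are not labelled as stand-alone powers. Under SAP 8.1.1 the later steps are declared with probability of about 0.918, 0.917 and 0.81 to 0.83, so roughly one trial in twelve stops at step a and nearly one in five does not complete the sequence. The re-estimation protects steps a to c. It does not protect step d, and its fourth power call cannot be reconciled with its own brackets.

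These results assume the SAP's planning means and pooled SDs, 75 analysed patients per arm, simple t-tests rather than the planned ANCOVA, and an endpoint correlation that the documents do not supply. Type I error is unaffected.

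**What to change.** In SAP 2.3.2:

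- Label the four figures as per-comparison powers, and restate OSDI 1.0% as about 0.88.
- Add the probabilities along the 8.1.1 sequence (about 0.918, 0.918, 0.917 and 0.81 to 0.83), with the correlation assumption stated.
- Replace power=.999 in the fourth call with the value the design delivers, 0.884. Keep .999 for b and c.
- State that the OSDI brackets are set by the 0.5% comparison. Even at 0.884 the fourth call returns 75 × (SD/8.71)², which is 92, 103 and 114 per arm at SDs of 9.64, 10.20 and 10.74, against 85, 95 and 105 allowed. The SAP should say whether that shortfall, a stand-alone power of about 0.86, is accepted.
- At the re-estimation, report the probability of passing through step b and through step d at the observed masked SDs.

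The cost is a wording change, a short calculation or simulation, and a less favourable stated figure. No test, alpha level or endpoint changes, and no extra patients are needed unless the sponsor chooses to close the step d shortfall.

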9.1.2 EXPANSION COHORT

Estimates for sample size calculations are from the final Cohort 1 interim analysis from Azura Clinical Protocol AZ201801. The mean response of 0.77 and a standard deviation for MGYLS of 2.28 units was observed for control and a mean response of 2.77 units and a standard deviation for MGYLS of 3.35 units was observed for AZR-MD-001 0.5%. A sample size of 45 subjects per group will have 90% power to detect a difference of 2.0 units between the active treatment group and the placebo group using a two-sample t-test at a significance level of 0.05. The standard deviation for Total OSDI was 6.31 units for control and 8.34 units for the high dose. A sample size of 58 subjects per group will have 90% power to detect a difference of 4.52 units between the active treatment group and the control group using a two-sample t-test at a significance level of 0.05. To allow for additional site to site variability the sample size per group will be increased to approximately 75 patients.

Multiplicity Consideration: To address the multiple primary endpoints defined in this study, the primary endpoints have been prioritized into a hierarchical structure. For example, in order to test the primary symptom endpoint of Total OSDI, the primary sign endpoint of MGYLS must be statistically significantly higher in the AZR-MD-001 treatment group compared to the vehicle treatment group using a two-sided significance level of 0.05 for a given concentration. The final order of the endpoints will be defined in the Statistical Analysis Plan (SAP) prior to unmasking the study. Using this strategy, the family-wise Type I error rate will be maintained at the 0.05 significance level for the two primary endpoints.

Interim Analysis (Primary efficacy endpoint for the US): An interim analysis is planned after the final enrolled patient completes the month 3 visit. Only an independent biostatistician will be unblinded to the treatment patients actually received and only summary efficacy and safety tables will be provided. Outcomes from this analysis will assist in the confirmation of the study power calculations and potentially as part of a rolling submission to global regulatory agencies.

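### The OSDI SD ranges for adding patients protect only the 0.5% comparison; at the range tops OSDI 1.0% power falls from 0.884 to about 0.86

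*SAP*

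**What the plan says.** SAP 2.3.1 states that "the sample size per group was increased to 75 randomized patients per arm". In SAP 2.3.2 the masked pooled SDs are "compared to the pooled standard deviations of 3.63 (MGYLS) and 8.71 (OSDI) from the integrated study", and the power at those reference SDs is given as "resulting in 0.918 for the MGYLS comparison of AZR-MD-001 0.5% to placebo, and >0.999 for the other comparisons". The purpose of adding patients is stated as follows: "Patients may be added up to the specified numbers, to maintain the current power of the study, if possible".

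Three bands follow, introduced as examples. The first reads "If the pooled standard deviation is 3.64-3.85 for MGYLS or 8.72-9.64 for OSDI total score, up to 30 additional patients may be randomized", which is 10 per arm. The second tops out at 4.07 (MGYLS) or 10.20 (OSDI) for 20 per arm, and the third at 4.29 or 10.74 for 30 per arm.

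The required number is then recalculated with four PROC POWER blocks that keep the integrated-study means fixed. The MGYLS 0.5% block carries "stddev=xxx sides=2 power=.918 npergroup"; the MGYLS 1.0% block and both OSDI blocks carry "stddev=xxx sides=2 power=.999 npergroup". SAP 8.1.1 makes OSDI 0.5% step (b) and OSDI 1.0% step (d) of the primary testing hierarchy.

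**The concern.** With the means fixed, keeping a comparison at its starting power requires n to grow with the square of the SD. The MGYLS bands behave that way from their 3.63 reference; the OSDI bands do not from 8.71. The same addition of 10, 20 or 30 per arm is tied to an SD excess of about 6%, 12% and 18% for MGYLS, but about 11%, 17% and 23% for OSDI.

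If the OSDI SD comes out high, the cap on additions may therefore be too small to restore the power of the OSDI comparison that has least to spare. The team would also not see this in advance, because the SAP credits both OSDI comparisons with power above 0.999.

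**Working it through.** **Inputs.** 75 per arm (SAP 2.3.1). Reference SDs 3.63 and 8.71 (SAP 2.3.2). Differences from the means in the pseudocode: MGYLS 0.5% 2.77 − 0.77 = 2.00; MGYLS 1.0% 3.79 − 0.77 = 3.02; OSDI 0.5% 8.36 − 0.81 = 7.55; OSDI 1.0% 5.33 − 0.81 = 4.52. The test is two-sided. The pseudocode gives no alpha; 0.05 is taken from Protocol 9.1.2 ("using a two-sample t-test at a significance level of 0.05").

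**Formula.** Power = P(|T| > t(0.975, 2n − 2)), where T is noncentral t with noncentrality δ = difference / (SD × √(2/n)).

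**Step 1: the printed powers at 75 per arm.**
- MGYLS 0.5%: 0.918, as printed.
- MGYLS 1.0%: 0.9990, as printed.
- OSDI 0.5%: 0.9995, as printed.
- OSDI 1.0%: δ = 4.52 / (8.71 × √(2/75)) = 3.178 against a critical value of 1.976, so power is 0.884. This does not match the printed figure.

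**Step 2: the printed band tops.**
- MGYLS 0.5% at target 0.918: SD 3.85, 4.07 and 4.29 need 85, 95 and 105 per arm, an exact match to the caps.
- OSDI 0.5% at target 0.999: SD 9.64, 10.20 and 10.74 need 85, 95 and 105 per arm, also an exact match.
- OSDI 1.0% at target 0.999: the same SDs need 233, 261 and 289 per arm, and SD 8.71 already needs 191.

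So the OSDI tops come from the third block alone. The MGYLS tops look variance-scaled because the 0.918 target equals the power at 75 per arm. The OSDI 0.5% target of 0.999 lies just under its 0.9995 at 75 per arm, and that slack widens the OSDI bands.

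**Step 3: what the bands deliver at their tops.**

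| OSDI SD | n per arm at cap | OSDI 0.5% at 75 | OSDI 0.5% at cap | OSDI 1.0% at 75 | OSDI 1.0% at cap | n per arm to hold 0.884 |
|---|---|---|---|---|---|---|
| 9.64 | 85 | 0.9975 | 0.9991 | 0.814 | 0.860 | 92 |
| 10.20 | 95 | 0.9945 | 0.9991 | 0.769 | 0.860 | 103 |
| 10.74 | 105 | 0.990 | 0.9991 | 0.726 | 0.859 | 114 |

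The last column agrees with 75 × (SD/8.71)² = 91.9, 102.9 and 114.0. The caps fall short by 7, 8 and 9 per arm.

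**Step 4: tops that would hold OSDI 1.0%.** 8.71 × √(n/75) gives 9.27, 9.80 and 10.31 for n = 85, 95 and 105, with OSDI 1.0% power 0.885 at each.

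**The case against.** A reader might infer that the OSDI tops are miscalculated, or that the rule cannot keep OSDI power at all. The documents support neither. The tops follow exactly from the SAP's own third block, and OSDI 0.5% meets its 0.999 target at every top; against its exact starting power it loses about 0.0004.

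Several further points limit the weight:
- The shortfall is worst at the band tops. At the band bottoms with the full addition, OSDI 1.0% power is 0.919 (SD 8.72, n = 85), 0.895 (9.65, n = 95) and 0.891 (10.21, n = 105), all above 0.884.
- The additions do help OSDI 1.0%: at SD 10.74 they raise it from 0.726 to 0.859.
- OSDI 1.0% is tested last, and only if steps (a) to (c) succeed.
- The pooled SD of 8.71 is a reference value. With the arm SDs in SAP Table 1 (8.39 and 6.31, root mean square 7.42), OSDI 1.0% power at 75 per arm is about 0.96, so 0.884 and 0.86 are not the power expected on the planning SDs.
- The bands are given as examples, and power is to be kept only where feasible.

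All of this stands except that the last point does not excuse the first two bands. There, 92 and 103 per arm lie within the overall maximum of 105, so holding the power was feasible and the band cap prevents it. Nor does the recalculation help: at a 0.999 target the fourth block exceeds every cap, so its result cannot guide the decision.

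**Conclusion.** The OSDI bands are sized for the 0.5% comparison and protect it. They do not maintain the current power of OSDI 1.0%, a primary comparison: 0.884 at the reference SD, about 0.86 at each band top with the full addition, a loss of about 2.5 percentage points at worst. The printed power above 0.999 for this comparison is wrong and hides the gap.

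This rests on the SAP's fixed mean differences, a common SD, equal arms, a two-sided 0.05 t-test and no allowance for covariate adjustment or dropout. It is a mismatch between the rule's stated purpose and what the rule delivers for one comparison, not an arithmetic slip in the band limits. It should be corrected before the masked SD review, but it does not threaten the design.

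**What to change.** In SAP 2.3.2:
- State that the OSDI bands are set to keep OSDI 0.5% at about 0.999, and that OSDI 1.0% power may fall to about 0.86 at the band tops even after the full addition.
- Replace the printed power for OSDI 1.0% with about 0.884 at SD 8.71 and 75 per arm.
- Set the fourth PROC POWER target to about 0.884. At the three tops it then returns 92, 103 and 114 per arm, so any shortfall against the cap is visible.

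These are wording changes, need no unmasking and add no patients.

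Optionally, also move the first two OSDI tops: 8.72–9.27 for up to 30 patients, 9.28–9.80 for up to 60, and 9.81–10.74 for up to 90. This holds OSDI 1.0% at 0.884 or better up to an SD of about 10.31, keeps the overall maximum at 90, and takes additions away from no SD that now permits them. The cost is that SDs of 9.28–9.64 and 9.81–10.20 would each permit 30 more patients than now, and OSDI 1.0% would still end at about 0.86 at SD 10.74. The third top should not be cut to 10.31: SDs of 10.32–10.74 would then have no listed addition, and without one OSDI 1.0% power at SD 10.74 is 0.726.
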